Participants will be removed from the study if they threaten the safety of CLH staff or other research participants, or of any other persons on the Johns Hopkins Bayview Campus.

g. Description of what happens to participants receiving therapy when study ends or if a participant's participation in the study ends prematurely.

Throughout the study, participants will be given referrals to services they might need (e.g., drug counseling, housing, medical, or employment services).

5. Inclusion/Exclusion Criteria

Inclusion criteria: a) 18 to 55 years old; b) homeless at the time of intake as defined by the McKinney-Vento Homeless Assistance Act (lacked a fixed, regular, and adequate nighttime residence including staying in a shelter, on the street, in an abandoned house or building, a car, or a park); c) unemployed; d) meet DSM V criteria for alcohol use disorder; and e) interested in obtaining employment. Exclusion criteria: a) report current suicidal/homicidal ideation; b) currently have nickel or other metal allergies, deep vein thrombosis, or leg ulcers where the SCRAM bracelet should be placed. Individuals excluded from the study will be linked with appropriate care as needed.

6. Drugs/ Substances/ Devices

NA a. The rationale for choosing the drug and dose or for choosing the device to be used.

NA b. Justification and safety information if FDA approved drugs will be administered for non-FDA approved indications or if doses or routes of administration or participant populations are changed.

NA c. Justification and safety information if non-FDA approved drugs without an IND will be administered.

NA

7. Study Statistics

a. Primary outcome variable.

Biologically-Verified Alcohol Abstinence (primary aim). Assess the effectiveness of *IPS Plus Abstinence-Contingent Wage Supplements* in promoting biologically-verified alcohol abstinence during the intervention. We will assess the number of days of alcohol abstinence (based on transdermal alcohol concentrations) during the 6 months after random assignment. Primary Hypothesis: Our primary hypothesis is that *IPS Plus Abstinence-Contingent Wage Supplements* will promote alcohol abstinence during the intervention after random assignment relative to Usual Care Control.

b. Secondary outcome variables.

Self-Reported Alcohol Use (secondary aim). Assess the effectiveness of *IPS Plus Abstinence-Contingent Wage Supplements* in reducing self-reported alcohol use during the intervention. We will use three self-report measures of alcohol use (based on TLFB) during the 30 days prior to each of the 6 monthly assessments during the year after random assignment. We will assess: 1) the percent of days abstinent from alcohol; 2) the average number of standard drinks per drinking day ingested; and 3) the percent of heavy drinking days (≥ 5 standard drinks per day for men and ≥ 4 standard drinks per day for women). Hypothesis: We expect that *IPS Plus Abstinence-Contingent Wage Supplement* participants will have less self-reported alcohol use during the intervention after random assignment relative to Usual Care Control.

Employment (secondary aim). Assess the effectiveness of *IPS Plus Abstinence-Contingent Wage Supplements* in promoting employment during the intervention. We will assess the number of days participants are employed during the 30 days prior to each of the 6 monthly assessments during the intervention after random assignment. Hypothesis: We expect that *IPS Plus Abstinence-Contingent Wage Supplements* will increase employment during the intervention after random assignment relative to Usual Care Control.

Post-Intervention Effects (secondary aim). Assess the effectiveness of IPS Plus Abstinence-Contingent Wage Supplements in promoting employment and abstinence from alcohol after the intervention ends. We will compare the groups on self-reported measures of alcohol use and employment at 6- and 12-month follow-up assessment time points after the intervention ends. Hypothesis: We expect that IPS Plus Abstinence-Contingent Wage Supplements may need to be maintained to promote long-term employment and abstinence from alcohol, and thus alcohol abstinence and employment may not be sustained after the intervention ends.

Economic Outcome Measures

Costs of Treatment (secondary aim). Assess the costs of treatment for Usual Care and IPS Plus Abstinence-Contingent Wage Supplements. We will assess the total cost per participant in both study groups. Hypothesis: We expect that treatment costs for IPS Plus Abstinence-Contingent Wage Supplements will be higher per person relative to Usual Care due to the IPS and wage supplements and because we expect that IPS Plus Abstinence-Wage Supplement participants will have greater treatment engagement.

[figure not shown]
Cost-Effectiveness (secondary aim). Assess the cost-effectiveness of IPS Plus Abstinence-Contingent Wage Supplements. Separate cost-effectiveness analyses will be conducted for the outcomes of alcohol use, employment, and homelessness. We will assess incremental cost-effectiveness ratio (ICER) by dividing the difference in costs of two interventions by the difference in the effects of the two interventions. The estimated ICER can be interpreted as dollars spent per unit of desired outcomes gained. Hypothesis: We expect that IPS Plus Abstinence-Contingent Wage Supplements will yield better ICERs for all measures.

Cost-Benefit (secondary aim). Assess the cost-benefit of IPS Plus Abstinence-Contingent Wage Supplements. We will perform a Cost-Benefit Analysis (CBA) to examine the monetized benefits relative to costs for the two groups. The economic outcomes are employment, crime, subsidized housing, and health care utilization. Hypothesis: We expect that IPS plus Wage Supplement will yield greater economic benefits in the 18-month post random assignment time period relative to the costs of Usual Care.

c. Statistical plan including sample size justification and interim data analysis.

Power Analysis

The primary outcome measures will be analyzed with a longitudinal binomial regression model using generalized estimating equations (GEE; Diggle & Diggle, 2002). We used Liu and Liang (Liu & Liang, 1997) to determine the total N required to detect differences between groups with 80% power. The adjacent figure shows the total number of participants (N) that would be required to detect a difference of 15% between the Usual Care Control and the IPS Plus Abstinent-Contingent Wage Supplement with the monthly assessments. The figure shows possible percentages for the Usual Care Control group because that value affects the sample size required. Fifteen percent is smaller than any difference in any Therapeutic Workplace study in which we promoted alcohol abstinence in homeless adults or cocaine abstinence in methadone patients (see figure in "Significance Section"). The horizontal red lines show the number of participants planned based on the number of participants randomized to the two groups without (top dashed red line) and after adjusting for the anticipated rates of missing data (10% missing, bottom solid red line). Based on this analysis, we need to randomize 130 participants (dashed red line) to ensure that we have sufficient sample sizes after adjusting for the rates of missing data. After adjusting for missing data (10% missing), this would yield a sample size of 117 participants (130 participants x 0.90 collected assessments = 117 participants). The adjusted sample size of 117 participants (solid red line) is a little more than the maximum number of required participants.

Main Statistical Analyses

Main analysis. All measures assessed repeatedly will be analyzed with a longitudinal binomial regression model. Within-person correlated outcomes will be handled using GEE (Zeger et al., 1988). Measures assessed once will be analyzed using logistic regression. The magnitude of effect for both

regression and GEE will be expressed using odds ratios with 95% CI. Analyses will include all randomized participants as intent-to-treat, and will be adjusted for pre-specified covariates used for stratification (Pocock et al., 2002). Tests will be two-sided and, because we have one primary outcome, alpha will be set at 0.05. Based on our previous experience, we expect rates of attrition at monthly visits to be low. If rates are higher than expected, we will use mixed effects models rather than GEE estimation, as the former has less strict assumptions regarding missing data (MAR, rather than MCAR). If it appears that the missing data are MNAR, then we will fit pattern mixture models as described by Hedeker & Gibbons (1997).

Missing data. We expect to collect >90% of assessments. Our approach to handle missing data will be to impute all missing values as the adverse outcome (e.g., alcohol positive). Model parameter estimates from this approach will be compared to a method without imputation. If these methods yield differing results, conclusions will need to be tentative, but results from both approaches will be reported in publications. To investigate sensitivity to missing values, participants with and without missing values will be compared by covariates and treatment assignment. If rates of missingness are higher than expected, we may use multiple imputation (Rubin, 1996) or pattern mixture models (Hedeker & Gibbons, 1997) to obtain unbiased estimates of treatment effects.

Consideration Of Sex And Other Variables In Moderating The Outcomes

We will conduct analyses to identify biological and other variables that moderate the outcomes of employment and alcohol abstinence. We will examine efficacy differences as a function of four variables assessed prior to random assignment by including interaction terms in our regression models: 1) Percent of days abstinent from alcohol (based on transdermal alcohol concentrations) prior to random assignment. 2) Opiate- and cocaine-negative urine samples from the assessment prior to random assignment. 3) Completed high school or obtained a GED; and 4) gender (male/female). Alcohol use and opiate/cocaine use prior to random assignment should be associated with higher rates of alcohol use and lower rates of employment during the 6 months after random assignment. We expect that high school completion or obtaining a GED will be associated with higher rates of employment. Gender is a key biological factor that may influence outcome. We also expect that the effect of IPS Plus Abstinence-Contingent Wage Supplements will be affected by these variables.

Balancing of potential moderators of treatment response via urn randomization merely ensures that the estimation of the treatment effect is unbiased. Balancing the randomization by these variables allows for them to be adjusted for in subsequent analyses. It does not take the place of these adjustments. Moderator analysis entails fitting a model with the main effects of treatment and the putative moderating variable, and their interaction. Likewise, balancing the variables during randomization does not take the place of fitting this interaction. For more discussion, see Pocock et al. (2002).

We will conduct similar analyses to identify variables that moderate outcomes on employment and alcohol use during the follow-up year after the interventions have ended. We will examine differences in outcomes during the follow-up year as a function of three variables assessed at the end of the intervention period by including interaction terms in our regression models: 1) Percent days abstinent from alcohol from the last 3 months under the study interventions; 2) percent of opiate- and cocaine-negative urine samples from the last 3 monthly assessments under the study interventions; 3) Highest hourly wage that each participant earned during the year after random assignment. We expect that alcohol and opiate/cocaine use during the last 3 months under the study interventions will be associated with higher rates of alcohol use and lower rates of employment during the follow-up year. We expect that the highest wage achieved under the study interventions will be associated with higher rates of employment and lower rates of alcohol use during the follow-up year.

Economic Analyses

Our economic evaluation will be done from the provider perspective.

Cost Analysis. We will derive cost estimates of intervention activities following an activity-based approach (Drummond et al., 2005; Gold et al., 1996; [name], [name] et al., 2004; [name] et al., 2005; [name], [name], et al., 2008). The total cost per participant of each intervention will be the sum of the cost for (1) staff labor, (2) building space, (3) wage supplements, and (4) supplies or materials. The total intervention cost for each participant is the cost per activity multiplied by the number of activities or services received by the participant. Taking the mean across participants in an intervention yields the mean per participant cost of that intervention. Treatment attendance will be captured in the modified Economic Form 90 AIR/ED. Standard addiction treatment costs will be drawn from the literature (e.g., [name] et al., 2004).

Cost-Effectiveness. Our Cost-Effectiveness Analysis (CEA) methodology (e.g., [name] et al., 1996, 1997, 2008; [name] et al., 2010) will combine the cost estimates (above) with intervention effectiveness measures. Separate cost-effectiveness analyses will be conducted for alcohol use, employment, and homelessness. The incremental cost-effectiveness ratio (ICER) is calculated by dividing the difference in costs of two alternatives by the difference in effects of the alternatives. The estimated ICER can be interpreted as dollars spent per unit of desired outcomes gained (e.g., \$300 per day abstinent). To gauge ICER sampling uncertainty, we will calculate the CI via nonparametric bootstrap methods (Indurkha et al., 2001; Briggs et al., 2006). We will estimate cost-effectiveness acceptability curves (CEAC) using nonparametric bootstrap methods (e.g., [name], et al., 2010; [name] et al., 2008). The CEACs show the probability that a treatment is cost-effective as a function of the policy maker's intrinsic valuation/willingness to pay for the clinical outcome.

Cost-Benefit. We will perform a Cost-Benefit Analysis to examine the monetized benefits relative to costs for the two study conditions. The key economic outcomes are employment, crime, and health care utilization assessed through the modified Economic Form 90 AIR/ED. The unit costs of these outcomes will be drawn from literature and public data sources (e.g., [name] et al., 2010).

Sensitivity Analysis. We will conduct sensitivity analyses to assess whether the economic results are affected by changes in model parameters. We will perform one-way sensitivity analyses in which we examine the effect of changing one of the model parameters while holding all other parameters constant. We will perform n -way sensitivity analyses in which n parameters of the model are varied jointly, holding other parameters constant.

Northern Michigan University

[name] and his team are at Northern Michigan University and will see and handle de-identified data for this protocol. The Northern Michigan University IRB has determined that [name] team's part in the research (analyzing de-identified data) is exempt. The letter from the Northern Michigan University IRB is uploaded below.

Here is NMU's Scope of Work for this project. Northern Michigan University will assist in preparing the data for analyses, and preparing and submitting manuscripts for publication and presentation. [name] is an Assistant Professor at Northern Michigan University. Under [name] supervision, research assistants will work with research staff at Johns Hopkins University School of Medicine to prepare the study data for analyses, and summarize and graph data for reports, publication, and presentation.

- d. Early stopping rules.

The protocol will be stopped if the Data Safety Monitoring Board recommends that the protocol be stopped due to unexpected rates of adverse events related to the protocol.

8. Risks

- a. Medical risks, listing all procedures, their major and minor risks and expected frequency.

There is essentially no risk above those of normal daily living associated with the training or work in the Therapeutic Workplace, with participation in the Individual Placement and Support program, with obtaining employment in community workplaces, with the incentive program, or with the data collection procedures used in these studies.

Side effects may occur from wearing a SCRAM bracelet. These include sores, open wounds, bruising, skin irritation and redness. Individuals who currently have nickel or other metal allergies, deep vein thrombosis, or leg ulcers may be more likely to experience side effects of wearing SCRAM.

Side effects may occur from wearing a BACtrack Skyn bracelet. These include skin irritation and redness.

- b. Steps taken to minimize the risks.

We will take several steps to minimize the risks associated with wearing SCRAM. Participants will be taught how to clean around and underneath their SCRAM bracelets to minimize the risk of developing side effects. Study staff will inspect the area surrounding participants' bracelets for skin redness, sores, bruising, or irritation when participants attend the research site to transmit the data stored on their bracelets. The bracelet may be loosened or switched to the other ankle. Participants who experience sores, open wounds, or severe bruising, irritation or redness will be seen by the study clinician, who will determine whether the participant may continue wearing SCRAM.

To protect confidentiality, all research participants are identified by participant identification codes (Participant IDs) consisting of their initials and sequentially-assigned participant numbers on most forms and data files, and not by their names. Picture ID cards are maintained by staff in a locked container, and kept in a locked, secured area when not in use. All research data are stored in locked areas accessible only to research staff and are not left unattended. Documents with confidential information are shredded before being discarded. Confidential information is never given to anyone outside of the research program without the explicit written permission of the research participant. Only selected designated staff members are approved to give confidential information out after obtaining explicit written permission from the participant. All research staff are trained in these procedures. We collect only general information about participant activities, legal and illegal. We do not collect information about specific illegal acts. In addition to these procedures, all persons who visit or work at the Center for Learning and Health are required to sign a confidentiality agreement, in which they agree not to disclose any confidential information that they may become aware of in the course of their time at the center. All participants are also invited to take a break and leave the workplace when visitors come to the Center for Learning and Health. To further protect confidentiality, we will obtain a confidentiality certificate from NIH to protect data collected in this study. Finally, to protect the confidentiality of participants who become employed in a community job, we will not interact with an employer unless the participant gives explicit written permission.

c. Plan for reporting unanticipated problems or study deviations.

Unanticipated problems or study deviations will be reported based on the guidelines of the Johns Hopkins University School of Medicine IRB.

d. Legal risks such as the risks that would be associated with breach of confidentiality.

There are risks that the confidential information we collect could be revealed to people not involved in the research such as a friend, relative, or an outside organization. This could be embarrassing to the participant if the participant wanted to keep participation in the study secret. The legal risks are limited because we collect only general information about participant activities, legal and illegal. We do not collect information about specific illegal acts. Thus, the risks associated with the assessments are not greater than the risks associated with routine psychological examinations or tests.

e. Financial risks to the participants.

There are no financial risks above those of normal daily living. Each participant is responsible for ensuring that the earning of incentives is reported properly to relevant government or private agencies and for determining whether or not the earnings will affect any benefits they might receive from those agencies.

9. Benefits

a. Description of the probable benefits for the participant and for society.

Benefits for the participant. All participants will have access to training in skills that could be useful in obtaining employment. Training will be provided in typing, keypad, general computer use, reading, math, GED preparation, and the use of Microsoft computer applications. IPS supported employment will be provided to help participants become employed. Since all participants in this study will be unemployed at the start of the study, this experience could help prepare participants for employment.

All participants will receive monetary incentives for participating in the Therapeutic Workplace during the first month of the study. Participants in the IPS Plus Abstinence-Contingent Wage Supplements group will get abstinence-contingent incentives for engaging in IPS supported employment and for obtaining and maintaining competitive employment. These incentives should increase participation in the Therapeutic Workplace, development of job skills, employment, and abstinence from alcohol. The earnings and payments could also have the benefit of providing a means of purchasing things that the individual would not otherwise be able to afford, including housing.

Benefits for society. The study will evaluate the effectiveness, cost-effectiveness, and cost-benefit of IPS Plus Abstinence-Contingent Wage Supplements in increasing employment and promoting long-term alcohol abstinence. This novel intervention could be an effective and economically sound means of promoting long-term alcohol abstinence and employment in homeless adults with alcohol use disorder, a population at considerable risk for a range of adverse outcomes including HIV because of

their poverty, unemployment and continued alcohol use. If participants complete the job training and use IPS supported employment services, they could become employed which could reduce their need for government services. If employed, they could also contribute to the overall tax revenue generated in their community. If the job skills training and employment program increases the employment of participants, it could reduce their poverty and reduce transmission of poverty to their children.

10. Payment and Remuneration

a. Detail compensation for participants including possible total compensation, proposed bonus, and any proposed reductions or penalties for not completing the protocol.

All incentives in this study will be provided by giving participants reloadable credits and adding incentives to the card when earned. Restrictions can be placed on these cards to restrict where they can be used to make purchases. We have been using these reloadable credit cards in our ongoing research and they have proved attractive to participants and convenient for staff to manage.

Phase 1 Induction and Training Incentives. All participants will be invited to enroll in the Therapeutic Workplace induction period for 1 week, where they can earn \$20 every weekday or a total of \$100. Participants who complete the induction period will be invited to enroll in the Therapeutic Workplace for about 3 weeks, where they can earn about \$32/weekday for participating in our job skills training program. In total, participants will be able to earn \$580 in Phase 1.

Phase 2 Abstinence-Contingent Wage Supplements. Participants in the Abstinence-Contingent Wage Supplement group will be able to earn wage supplements of up to \$8 per hour for up to 40 hours per week for 24 weeks. In total, participants in the Abstinence-Contingent Wage Supplement group will be able to earn up to \$7,680 in wage supplements.

Participant payment for wearing alcohol biosensor. Participants can earn daily pay for wearing their wearable alcohol biosensor. Participants can earn \$0.25 per hour for wearing their alcohol biosensor and can earn a \$5 bonus for wearing their alcohol biosensor for at least 18 hours per day. However, to receive the daily payment participants must receive permission to remove their bracelet by sending research staff a photo or video of themselves wearing the bracelet after they put the bracelet back on. In total, participants could earn a maximum of \$11 per day for wearing their biosensor.

Participant payment for assessments. Assessments will be conducted for all participants at intake to determine eligibility and characterize the population, immediately prior to random assignment, every 30 days throughout the 6-month intervention evaluation period after random assignment and then at 6 and 12 months after the end of the intervention evaluation period. Participants will be paid \$30 for the intake and monthly assessments during the 1-month training period and the 6-month intervention evaluation period, and \$50 for the assessments conducted 6 and 12 months after the end of the intervention evaluation period. In total, participants will be able to earn up to \$340 for completing the assessments in this study.

Participant referral fees. As in our previous studies, participants will have the optional opportunity to earn incentives for referring people who are interested in the study. If a referral attends the initial screening appointment and completes the necessary assessments, the participant who referred the person will receive up to \$20. If a referred person enrolls in the main study, the participant who referred the person will receive up to \$40 for making the referral.

Device Return. To help ensure that participants return their wearable alcohol biosensor bracelets after their study participation ends, participants will be able to earn \$100 for returning the bracelet to our staff.

11. Costs

a. Detail costs of study procedure(s) or drug (s) or substance(s) to participants and identify who will pay for them.

There will be no costs to participants for any services or treatment provided in this study. All procedures in the study will be paid for out of grant funds.

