To increase the chance that we engage participants, upon enrollment, participants will be invited to participate in a 1-week Therapeutic Workplace induction period. During the induction period, participants will be asked to maintain contact with Therapeutic Workplace staff by calling or texting staff every weekday. We have used similar induction procedures in our prior studies to successfully engage participants. Participants will be able to earn \$20 per weekday for maintaining contact with our staff during the induction period. Participants who complete the 1-week induction will be given a wearable alcohol biosensor, invited to call in to the Therapeutic Workplace every weekday for 3 weeks, and can earn about \$32/weekday for participating in our job-skills training program. Participants will be taught about the Therapeutic Workplace. Some or all of the training may be given through a computer-based training program. We may also evaluate the effectiveness of the training program by giving participants tests before and after they complete parts or all of the training program. We may re-administer the test at the end of the intervention to measure retention. Each Therapeutic Workplace participant will have a participant ID, which will be used to enter participant drug and alcohol testing results into our therapeutic workplace software, automatically implement any responses to drug and/or alcohol use based on testing results, and to automatically calculate participant daily pay based on compliance with drug and/or alcohol contingencies. Participants will be required to wear their wearable alcohol biosensor (SCRAM or BACtrack Skyn), which will record transdermal alcohol concentrations. Participants will be given separate care and use information about their wearable alcohol biosensor. Participants who wear a SCRAM bracelet will need to come to the Therapeutic Workplace (about every 30 days) so that the data stored on their bracelet can be transmitted to SCRAM_{NET} and accessed by our research staff. Participants who wear a BACtrack Skyn bracelet will need to transmit the data stored on their bracelet via Bluetooth using a smartphone. At the end of Phase 1, participants will be randomly assigned to groups.

Experimental Design

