Participants (N = 130) will be randomly assigned to a Usual Care Control or IPS Plus Abstinence-Contingent Wage Supplements group. Computerized urn randomization (Wei & Lachin, 1988) will balance groups on characteristics that may influence outcome: (1) percent of days abstinent from alcohol (assessed by transdermal alcohol concentrations prior to random assignment; \geq rolling median, Y/N); (2) evidence of opiate and cocaine use from the assessment prior to random assignment (Y/N); (3) completed high school or obtained a GED (Y/N); and (4) gender (male/female). Participants will be stratified by alcohol and drug use because they should predict alcohol abstinence during the intervention period. High school completion or GED should be associated with employment. Participants will be stratified by gender to balance the two groups on a key biological factor that may influence outcome.

Individual Placement and Support (IPS) & Abstinence-Contingent Wage Supplement Group

This group will receive the full intervention being evaluated in this study for 6 months.

Individual Placement and Support (IPS). After Phase 1, participants will be offered the IPS model of supported employment for 6 months. IPS involves rapid job search, promotes competitive employment, and provides job supports and benefits counseling.

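### Biosensor wear before randomization is not a covariate in the primary model, although wear enters the scored outcome; adding it costs almost nothing and gains precision only if wear is well below 90% and persists

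*Combined protocol and SAP*

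**What the plan says.** - **Outcome (7.a).** "We will assess the number of days of alcohol abstinence (based on transdermal alcohol concentrations) during the 6 months after random assignment".
- **Missing data (7.c, Missing data).** The approach is to "impute all missing values as the adverse outcome", with alcohol positive as the example. Also: "Model parameter estimates from this approach will be compared to a method without imputation". If missingness is higher than expected, multiple imputation or pattern mixture models may be used.
- **Adjustment (7.c, Main analysis).** Analyses "will be adjusted for pre-specified covariates used for stratification". No other covariate is named for the main model.
- **The factors (4.a, Experimental Design).** "Computerized urn randomization (Wei & Lachin, 1988) will balance groups on characteristics that may influence outcome". They are percent of days abstinent by transdermal reading before randomization (split at a rolling median), evidence of opiate and cocaine use, high school or GED, and gender.
- **Device before randomization (4.a, Therapeutic Workplace and Job-Skills Training).** After a 1-week induction the device is issued for the remaining 3 weeks of Phase 1. "Participants will be required to wear their wearable alcohol biosensor (SCRAM or BACtrack Skyn), which will record transdermal alcohol concentrations".
- **Wear is observable (4.a, Abstinence monitoring; 10.a).** SCRAM records infrared signals and temperature, and Skyn records temperature, in each case to detect removal. Wear is paid by the hour, with a bonus for "wearing their alcohol biosensor for at least 18 hours per day".
- **Who is randomized (4.b).** Those who attend the end-of-Phase-1 assessment and are willing to keep wearing a device.

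The plan does not define a worn day, and does not say how unworn days before randomization enter the first urn factor.

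**The concern.** If a missing day is scored alcohol positive, a day counts as abstinent only when the device was worn and read negative. The scored outcome is then the product of two behaviours, wearing and not drinking. The covariates address drinking and general prognosis, but none measures wearing directly.

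Persistent differences between people in wear therefore go into the residual variance of the primary comparison, and a chance imbalance in habitual wear moves the estimate within its sampling error. A baseline measure that predicts later wear would remove part of both. Section 4.a justifies the balancing factors by their possible influence on outcome, and on this scoring wear meets that criterion by construction. What is at stake is precision with 130 participants.

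**Working it through.** **1. The plan's own figure.** 130 × 0.90 = 117, as stated in 7.c (Power Analysis). The required N is shown only in a figure not available here, so I used the Liu–Liang formula for a repeated binary outcome:

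N = 2(z₁ + z₂)² [p₀q₀ + p₁q₁] [1 + (m − 1)ρ] / (m d²)

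From the plan: m = 6 monthly assessments, d = 0.15, two-sided alpha 0.05, power 80%. Assumed: 1:1 allocation, worst case 42.5% against 57.5%, and ρ = 0.2.

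N = 2 × 7.849 × 0.48875 × 2 / (6 × 0.0225) = 113.7

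At ρ = 0.21 this is 116.5. So 117 as slightly above the maximum fits ρ of about 0.20 to 0.21. The text does not confirm that value, and nothing here suggests an error in the sample size.

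**2. What a covariate could be worth.** If baseline wear explains a further share R² of the person-level variance, required N becomes 113.7 × (1 − R²). Power is for 130 participants with complete data.

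| R² | Required N | Power at 130 |
|---|---|---|
| 0 | 113.7 | 85.0% |
| 0.02 | 111.4 | 85.7% |
| 0.05 | 108.0 | 86.7% |
| 0.10 | 102.3 | 88.5% |
| 0.20 | 90.9 | 91.8% |

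The documents do not give R². It depends on the wear rate and on how well baseline wear predicts later wear, so both were varied.

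**3. Linear model, simulated.** Settings: 130 participants, 21 baseline and 180 follow-up days, outcome = days worn and abstinent / 180, 15-point effect. Assumed: mean abstinence 0.55 with between-person SD 0.30; wear mean/SD 0.90/0.15, 0.80/0.25 or 0.70/0.30; abstinence correlation between phases 0.6; wear–abstinence correlation 0.3. The model holds arm and the median flag, with and without the baseline wear proportion. The ratio is variance without wear over variance with it, and the reduction is 1 − 1/ratio.

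| Mean wear | Ratio, wear correlation 0.3 to 0.7 | Reduction at the upper end |
|---|---|---|
| 90% | 0.99 to 1.06 | 1 − 1/1.06 = 5.7% |
| 80% | 1.00 to 1.15 | 1 − 1/1.15 = 13.0% |
| 70% | 1.01 to 1.21 | 1 − 1/1.21 = 17.4% |

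These ratios take the first urn factor over worn days only. If unworn baseline days count as non-abstinent there, the ratio is 0.99 to 1.06 across all wear levels, because that factor already carries part of the wear information.

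**4. Closer to the planned scale.** A fractional logit model with robust standard errors, 4,000 trials per setting, person-level SD calibrated to 0.29, urn factor 1 in both models and the other three left out. Power without → with baseline wear:

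| Wear | Wear correlation | Factor 1 over worn days | Unworn = non-abstinent in factor 1 |
|---|---|---|---|
| 90% | 0.3 | 90.3 → 90.2% | 90.2 → 89.9% |
| 90% | 0.7 | 90.6 → 91.1% | 90.9 → 90.8% |
| 80% | 0.3 | 88.7 → 88.8% | 88.2 → 88.0% |
| 80% | 0.7 | 87.9 → 91.4% | 90.7 → 90.9% |
| 70% | 0.3 | 84.2 → 85.3% | 85.5 → 85.4% |
| 70% | 0.7 | 86.6 → 94.0% | 89.7 → 92.0% |

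Both models show the same pattern: little or nothing at 90% wear or at low correlation, and a useful gain at 70 to 80% wear with a correlation near 0.7, mostly when factor 1 is taken over worn days.

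**The case against.** The strongest reply is that the plan expects about 10% missing, and at 90% wear the covariate changes power by −0.3 to +0.5 points in the logit simulation. That stands as arithmetic. However, the figure in 7.c concerns assessments collected, and the attrition statement concerns monthly visits. Neither is a rate of biosensor days worn, so 70 to 80% wear cannot be excluded.

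Other points that stand, wholly or in part:

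- The gain depends on an undocumented correlation. At 0.3 it is essentially nil at 90% and 80% wear and about 1% of variance at 70%.
- If missing = positive also applies at baseline, the first urn factor carries some wear information, though only as a yes/no split.
- With poor wear the plan may turn to multiple imputation or pattern mixture models, and it always reports an analysis without imputation. The switch is optional, and the covariate can serve in those models too.
- The planned measure is an odds ratio. Its standard error on the log scale hardly moves at 90% wear (0.200 to 0.200–0.201). A further covariate also slightly changes the conditional odds ratio being estimated, as the four planned factors already do.
- Willingness to keep wearing the device is a condition of randomization, which may narrow the range of baseline wear. Section 10.a does not say that hourly wear pay applies in Phase 1, and later wage supplements in one arm depend on wear. Either could weaken prediction.

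A reader might infer that substantial precision is being thrown away, or that the primary effect is biased by the omission. The documents support neither. The size cannot be derived from them, and randomization protects the comparison from baseline differences in wear. Nor would the covariate remove a wear difference that arm-specific pay creates after randomization. Section 4.a also gives a 3-week opportunity to wear the device, not 21 recorded days per person.

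**Conclusion.** The point holds as a minor efficiency improvement. On the natural reading of 7.c, wear forms part of the scored outcome. A pre-randomization measure of it can be derived from device data, and the adjustment set has no direct measure of it.

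Under assumed wear correlations of 0.3 to 0.7, the variance of the treatment effect in a linear model falls by about 0 to 6% at 90% wear, 0 to 13% at 80% and 1 to 17% at 70%, and by at most about 6% if unworn baseline days already count as non-abstinent. The conclusion rests on three assumptions: unworn days are treated as missing, and so as positive; wear is well below 90%; and baseline wear predicts later wear. If either of the last two fails, there is essentially nothing to gain and one degree of freedom to lose.

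**What to change.** In 7.c (Main analysis), before outcomes are examined by arm:

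1. Add the proportion of pre-randomization biosensor days worn, as one continuous covariate, to the primary model beside the four urn factors.
2. Use the same term in the model without imputation and in any multiple imputation.
3. Define a worn day once and apply the definition to baseline and follow-up.
4. State how unworn baseline days enter the first urn factor.

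The cost is a few sentences and one degree of freedom. Randomization is unchanged, and no new data are needed, because the first urn factor already relies on the same device records. The text should describe the term as a precision covariate, so that it is not taken to deal with wear differences between arms during the intervention.
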